6.3 Measures to Minimise Bias: Randomization and Blinding

The Investigator(s) will:

- 1. Obtain signed informed consent from the potential subject before any study specific procedures are performed.
- 2. Assign the potential subject a unique enrolment number (which begins with an 'E') via IWRS.
- 3. Determine subject eligibility.
- 4. Assign the eligible subject unique randomization code via IWRS.
- 5. Subjects will be allocated to receive tezepelumab or placebo in a 1:1 ratio and according to the stratification factors listed in Section 4.1. Randomization numbers will be grouped in blocks. If a subject withdraws from the study, then his/her enrolment/randomization code cannot be reused. Withdrawn subjects will not be replaced.

Specific information concerning the use of the IWRS will be provided in a separate manual.

Procedures for handling incorrectly enrolled or randomized subjects

Subjects who fail to meet the eligibility criteria should not, under any circumstances, be randomized or receive study medication. There can be no exceptions to this rule. Subjects who are enrolled, but subsequently found not to meet all the eligibility criteria must not be randomized or initiated on treatment and must be withdrawn from the study.

Where a subject does not meet all the eligibility criteria but is randomized in error, or incorrectly started on treatment, the Investigator should inform the AstraZeneca study physician immediately, and a discussion should occur between the AstraZeneca study physician and the Investigator regarding whether to continue or discontinue the subject from treatment. Study treatment must be discontinued in all cases where continued treatment is deemed to pose a safety risk to the patient and AstraZeneca study physician must ensure the decision is appropriately documented. Subjects that are discontinued from treatment should be followed up according to the options described in Section 7.1.1.

In those cases where continuation of the study therapy is judged not to present a concern related to safety and disease management, the rationale for continuing study therapy must also be clearly documented.

Methods for assigning treatment groups

Randomization codes will be assigned strictly sequentially in each stratum as subjects become eligible for randomization.

The randomization code will be assigned from a randomization list prepared by a computerized system provided by \overline{PPD} on behalf of AZ (AZRand). All subjects will be stratified at randomization by region and number of exacerbations in the 12 months prior to Visit 1 (or re-screening Visit 1) (2 vs \geq 3).

In order to achieve the assumed exacerbation rates used to determine sample size, it is expected that approximately 30% of subjects will have had at least 1 severe exacerbation (an exacerbation resulting in hospitalization) within 12 months prior to Visit 1 (or re-screening Visit 1) and approximately 40% of subjects will have had \geq 3 exacerbations within 12 months prior to Visit 1 (or re-screening Visit 1). (Refer to Section 4.1)

Consideration will be given to closing the Interactive Web Response System (IWRS) randomization for a subgroup [by region or overall] to ensure that approximately 20% of the subjects will be targeted to have ≥ 300 eosinophils/ μ L, 40% of the subjects between ≥ 150 to < 300 eosinophils/ μ L and a maximum of approximately 40% of the subjects with < 150 eosinophils/ μ L at enrolment.

Ensuring blinding

This is a double-blind study in which tezepelumab and placebo are not visually distinct from each other. All packaging and labelling of IP will be done in such way as to ensure blinding for all sponsor and investigational site staff. Neither the subject nor any of the Investigators or sponsor staff who are involved in the treatment or clinical evaluation and monitoring of the subjects will be aware of the treatment received. Since tezepelumab and placebo are not

visually distinct, IP will be handled by a qualified person (e.g., pharmacist or study nurse) at the site.

An AstraZeneca site monitor will perform IP accountability. In the event that the treatment allocation for a subject becomes known to the Investigator or other study staff involved in the management of study subjects or needs to be known to treat an individual subject for an AE, the sponsor must be notified immediately by the Investigator and, if possible, before unblinding.

The following personnel will have access to the randomization list:

- Those carrying out the packaging and labelling of IP
- Those generating the randomization list
- Personnel at the IWRS company
- Supply Chain Management department
- Patient Safety department at AstraZeneca
- Bioanalytical lab performing the PK sample analysis
- Those involved in the reporting and reviewing the unblinded IDMC presentations

The information in the randomization list will be kept from other personnel involved in the conduct of the study and in a secure location until the end of the study.

No other member of the extended study team at AstraZeneca, or any Contract Research Organization (CRO) handling data, will have access to the randomization scheme during the conduct of the study until after the primary database lock.

Methods for unblinding

Individual treatment codes, indicating the treatment randomization for each randomized subject, will be available to the Investigator(s) and delegate(s) at the study sites from the IWRS. Routines for this will be described in the IWRS user manual that will be provided to each site.

The treatment code should not be broken except in medical emergencies when the appropriate management of the subject requires knowledge of the treatment randomization. The Investigator should document and report the action to AstraZeneca, without revealing the treatment given to subject to the AstraZeneca staff.

AstraZeneca retains the right to break the code for SAEs that are unexpected and are suspected to be causally related to an IP and that potentially require expedited reporting to regulatory authorities. Treatment codes will not be broken for the planned analyses of data until all decisions on the evaluability of the data from each individual subject have been made and documented and until primary database lock after last subject completes week 52 has been documented.

6.4 Compliance to IP

Any change from the dosing schedule or dose discontinuations should be recorded in the eCRF.

The IP Storage Manager is responsible for managing the IP from receipt by the study site until the destruction or return of all unused IP. The date and time of all IP administrations, as well as any missed doses with the reason for drug interruption, should be recorded in the appropriate section of the eCRF.

6.5 Concomitant Therapy

Information about all COPD medications given within the 12 months prior to Visit 1, all medications for other indications given in the 3 months prior to Visit 1, COVID-19 vaccine given at any time, and all concomitant medications given during the study, with reason for the treatment, will be collected by the Investigator/authorized delegate at each visit (as shown in Table 1 and Table 2) and recorded in the eCRF.

The subject's usual pre-study triple inhaled therapy (medium to high dose ICS/LABA/LAMA) formulation, dose and regimen, and any other additional allowed COPD medications that may have been taken prior to enrolment, should be continued without any change throughout the enrolment, run-in, treatment and follow-up period as outlined below.

As theophylline has a narrow therapeutic window, please note that subjects on maintenance treatment with theophylline should have blood concentration levels within therapeutic range documented within 8 weeks prior to Visit 1 (see Table 6). If this is not documented before signing the informed consent, it can be obtained after informed consent has been given or as part of the Visit 1 procedures. The sample can be analyzed at the central or local lab as applicable. Theophylline blood levels greater than 12mg/dl should be managed according to local standards of care and the Investigator's judgment and discussed with AZ study physician prior to randomization. It is recommended that additional increments in dose are evaluated with blood levels. Investigator can use their clinical judgement about the therapeutic range of theophylline levels on the basis of sampling time and other factors that may impact the results.

Any medication or vaccine including over-the-counter or prescription medicines, vitamins, and/or herbal supplements that the subject is receiving at the time of enrolment or receives during the study must be recorded along with:

- Reason for use
- Dates of administration including start and end dates

Table 6 - Allowed, Restricted and Prohibited Medications

Medication	Allowed/ Restricted/ Prohibited	Details
Background (maintenance) COPD medication (ICS/LABA/LAMA)	Allowed	Documented treatment with medium or high dose ICS at a total daily dose corresponding to >250µg fluticasone propionate dry powder formulation equivalent and a LABA and LAMA for COPD throughout the year prior to enrolment (Visit 1) and throughout the study. The dose of ICS should be stable 3 months prior to V1 and throughout the study. See inclusion criterion 7. ICS in a separate, single device is permitted if all the following criteria are met: - it is administered at the same dose and schedule as in the fixed dose combination product; - it is not given in combination with a LAMA alone. If an Investigator decides to switch a subject who is on an ICS in a separate single device to a fixed-dose combination device therapy, this should be done at Visit 1 and the ICS component must remain at the same dose and schedule as used in the 3 months prior to Visit 1 (provided dose and regimen are locally approved for COPD). Nebulized budesonide is accepted as part of maintenance therapy if the dosing regimen is equivalent to that of budesonide approved as part of a combination product for COPD (e.g., for budesonide/formoterol combination 320mcg/9mcg BID equivalent dose of nebulized budesonide is 0.5mg BID [GOLD 2019]

Medication	Allowed/ Restricted/ Prohibited	Details
		Nebulized LABA is accepted as part of maintenance therapy.
		Twice daily triple inhaled (ICS/LABA/LAMA) medications should be withheld at least 12 hours prior to scheduled spirometry at site.
		Once daily triple inhaled (ICS/LABA/LAMA) medications should be withheld at least 24 hours prior to scheduled spirometry at site
		Twice daily LABA or LAMA-containing therapies should be withheld for at least 12 hours prior to scheduled spirometry at site.
		Once daily LABA or LAMA-containing therapies should be withheld for at least 24 hours prior to scheduled spirometry at site.
Additional ICS on top of COPD ICS maintenance medication	Restricted	Can only be given concomitantly with systemic steroids during acute COPD exacerbation treatment while at site or other health care provider. Additional use of ICS outside of this is not allowed.
Systemic corticosteroids (tablets or injections)	Restricted	Prohibited as maintenance treatment within 3 months prior to Visit 1 and throughout the study. Allowed to treat a COPD exacerbation or an AE where there is no alternative treatment available, for no more than 14 days.
		If treatment duration is expected to exceed 14 days, the AstraZeneca study physician must be contacted.
Maintenance SABA (short-acting β2-	Prohibited if	Please see below. Use on their own, or for

Medication	Allowed/ Restricted/ Prohibited	Details
agonists) administered by either MDI or nebulizer	administered as part of maintenance double/triple therapy.	step-up or step-down are not allowed.
SABA (short-acting β2-agonists administered by an MDI or nebulizer)	Allowed as rescue medication and for treatment of acute COPD exacerbation. Prohibited if administered as maintenance medication or in a scheduled dose.	Prophylactic use of SABA in the absence of symptoms is discouraged. However, if deemed necessary by the subject and Investigator (e.g., prior to planned exercise), it can be used, but such use of prophylactic inhalations should be documented in the medical notes and recorded in the eCRF. Use of SABA is to be avoided 6 hours before a scheduled ECG, FeNO and spirometry assessment. Occasions (# of times used) where SABA was administered via an MDI will be recorded separately from the nebulized inhalations in the eDiary.
Maintenance SAMA (short acting muscarinic antagonists = short acting anticholinergics administered by MDI or nebulizer)	Prohibited if administered as part of maintenance double/triple therapy.	Please see below. Use on their own, or for step-up or step-down is not allowed.
SAMA (short acting muscarinic antagonists = short acting anticholinergics administered by MDI or nebulizer)	Allowed as rescue medication and for treatment of acute COPD exacerbation. Prohibited if	Prophylactic use of SAMA in the absence of symptoms is discouraged. However, if deemed necessary by the subject and Investigator (e.g., prior to planned exercise), it can be used, but such use of prophylactic inhalations should be documented in the medical notes and recorded in the eCRF.

Medication	Allowed/ Restricted/ Prohibited	Details
	administered as maintenance medication or in a scheduled dose.	Use of SAMA is to be avoided 6 hours before a scheduled ECG, FeNO and spirometry assessment. Occasions (# of times used) where SAMA was administered via MDI will be recorded separately from the nebulized inhalations in the eDiary.
SABA and SAMA combination products	Allowed as rescue medication and for treatment of acute COPD exacerbation. Prohibited if administered as maintenance medication or in a scheduled dose.	Prophylactic use of SABA and SAMA combination product in the absence of symptoms is discouraged. However, if deemed necessary by the subject and Investigator (e.g., prior to planned exercise), it can be used, but such use of prophylactic inhalations should be documented in the medical notes and recorded in the eCRF. Use of SABA and SAMA combination product is to be avoided 6 hours before a scheduled ECG, FeNO and spirometry assessment. Occasions (# of times used) where SABA and SAMA combination product was administered via MDI will be recorded separately from the nebulized inhalations in the eDiary.
Antitussives prn	Allowed	
Mucolytics	Allowed	
Antihistamines prn	Allowed	
Dermal topical steroids, intra-articular, nasal steroids, topical ophthalmic and otic	Allowed	

Medication	Allowed/ Restricted/ Prohibited	Details
corticosteroids		
Xanthines	Restricted	Allowed only if on maintenance treatment for 12 months and on a stable dose for 3 months prior to enrolment (Visit 1). Allowed in a dose equivalent to theophylline ≤400mg q day. For doses greater than 400 mg, the dose must be stable and theophylline blood levels should be confirmed to be equal to or below 12 mg/dl, within 8 weeks prior to Visit 1 or during the screening period. Theophylline blood levels greater than 12mg/dl should be managed according to local standards of care and the Investigator's judgment and discussed with AZ study physician. It is recommended that additional increments in dose are evaluated with blood levels. Twice daily xanthines should be withheld for
		at least 12 hours prior to scheduled spirometry at site. Once daily xanthines for at least 24 hours prior to scheduled spirometry at site.
Antibiotics	Restricted	Allowed to treat COPD exacerbations and/or AEs. Antibiotics to treat a COPD exacerbation should not be used for more than 14 days. If treatment duration is expected to exceed 14 days, the AstraZeneca study physician must be contacted. Chronic use (>3wks) and use for the prevention of COPD exacerbations is

Medication	Allowed/ Restricted/ Prohibited	Details
		disallowed, unless the patient is on stable dose and regimen for ≥9 months prior to randomization and has had ≥2 COPD exacerbations while on stable therapy (see exclusion criterion 24, Section 5.2). In all other cases of chronic use, ≥6 weeks wash-out period should be in place after the last dose of antibiotic and prior to randomization.
Allergen immunotherapy	Restricted	Allowed, if on stable therapy for at least 2 months prior to date of Visit 1 with no anticipated change during the screening and the treatment period. These should not be administered on the same day as IP administration.
Inactive/killed vaccinations (e.g., inactive influenza)	Restricted	Allowed, except - within 5 days before or after any IP dosing visit - within 3 weeks before sputum collection (Visit 3) for subset of subjects only 3 weeks prior to EOT visit for sub-study subjects only
COVID-19 vaccinations	Restricted	COVID-19 vaccination is allowed, provided it is not administered within 28 days before and 14 days after IP administration. Administration timing of COVID-19 vaccination should be discussed with the AstraZeneca Study Physician. If participant receives COVID-19 vaccine less than 14 days before the next scheduled dose of study intervention, the study intervention administration should be rescheduled or skipped to ensure the next study intervention dose is at least 28 days after the vaccine

Medication	Allowed/ Restricted/ Prohibited	Details
		administration.
		COVID-19 vaccination schedule should follow country-specific health authority guidelines. Vaccination against COVID-19 should be planned in advance to ensure the study intervention dosing/COVID-19 vaccination intervals are maintained. At every study visit during the treatment
		period, the investigator must ask if the participant has received or is planning to receive a COVID-19 vaccination. This is to ensure that the required time interval for study intervention dosing (mentioned above) is maintained.
		As these intervals might change, please discuss with AstraZeneca Study Physician for the most current recommended time interval prior to any vaccine dose Refer to section 8.2.10
Roflumilast (Daxas®, Daliresp®)	Restricted	Allowed only if on maintenance treatment for 12 months, on a stable dose for 3 months prior to enrolment (Visit 1), and only if locally approved for COPD.
		If roflumilast is discontinued at Visit 1, approximately 7 days must elapse before performing spirometry testing at Visit 2.
Leukotrienes (LTRA)	Restricted	Restricted for at least 24 hours prior to scheduled spirometry at site.
Immunoglobulin and Blood products	Prohibited	Prohibited within 30 days prior to enrolment (Visit 1) and throughout the treatment period.

Medication	Allowed/ Restricted/ Prohibited	Details
Medications containing ephedrine	Prohibited	From Visit 3 and throughout the treatment period.
Live attenuated vaccines	Prohibited	Prohibited within 30 days prior to Visit 3, during the treatment period and for 16 weeks (5 half-lives) after the last dose of IP.
Omalizumab, denosumab or any other monoclonal or polyclonal antibody therapy (e.g., gamma globulin)	Prohibited	Prohibited if taken for any reason within 4 months or 5 half-lives (whichever is longer) prior to Visit 1 and during the study (even if the subject has discontinued IP).
Systemic immunomodulators and immunosuppressive medication (including but not limited to methotrexate, cyclosporine, any experimental anti-inflammatory therapy	Prohibited	Prohibited within 3 months prior to Visit 1 and throughout the study or 4 weeks after the last dose of IP. Refer to Systemic corticosteroids (tablets or injections) for further restrictions.
Long term oxygen therapy (LTOT)	Restricted	Prohibited with signs and/or symptoms of cor pulmonale and/or right ventricular failure or receiving LTOT >4.0 litres/minute (L/min), or saturation <89% despite LTOT. During the treatment phase, any increase in maintenance oxygen therapy up to 4 L/min is allowed, based on investigator's judgement.
Investigational non-biologic products	Prohibited	Prohibited within 30 days or 5 half-lives whichever is longer prior to Visit 1 and during the study.

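### The theophylline action level is printed as 12 mg/dl (120 mg/L) in three places, very likely a tenfold unit slip for 12 mg/L; as printed it would almost never operate at maintenance doses

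*Protocol*

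**What the plan says.** The limit has two uses in the protocol.

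- **Trigger for discussion.** Section 6.5 says: "Theophylline blood levels greater than 12mg/dl should be managed according to local standards of care". It adds investigator judgement and requires that such levels be "discussed with AZ study physician prior to randomization". Table 6 (Xanthines) repeats the instruction with the same unit, without the reference to randomization.
- **Level condition by dose.** Table 6 first states: "Allowed in a dose equivalent to theophylline ≤400mg q day". Above that dose it keeps a stability requirement: "For doses greater than 400 mg, the dose must be stable". It then sets a level condition, to be met in the 8 weeks before Visit 1 or in the screening period: "theophylline blood levels should be confirmed to be equal to or below 12 mg/dl".

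The unit is mg/dl each time. Neither document prints the limit in mg/L or µg/mL, and neither gives a numeric therapeutic range. Section 6.5 justifies the check by the drug's narrow therapeutic window. Section 6.5 and the note to inclusion criterion 11 both recommend a documented level within the therapeutic range; if none exists, "it can be obtained after informed consent has been given or as part of the Visit 1 procedures". Section 6.5 also says: "Investigator can use their clinical judgement about the therapeutic range of theophylline levels".

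**The concern.** A limit justified by a narrow window, and applied specifically to doses above 400 mg/day, should be one that some patients on such doses would cross. If 120 mg/L lies above almost every level that maintenance dosing can produce, neither use of the number separates anyone. A site that converts its laboratory's units literally would clear a subject whom the sponsor probably meant to be discussed. A site that silently reads mg/L would apply a different rule. What is at stake is a concomitant-medication safety check and its consistent application across sites, not the efficacy analysis.

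**Working it through.** **Unit conversion.** 12 mg/dl × 10 dl/L = 120 mg/L, exactly ten times 12 mg/L. The protocol gives no derivation of the limit to reproduce.

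**Inputs from the protocol.** The limit; the 400 mg/day dose boundary (Table 6); the minimum weight of 40 kg (inclusion criterion 13).

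**Assumptions, not in the documents.** Clearance (CL) 0.4 to 5 L/h, where the lower end equals 0.01 L/h/kg × 40 kg; example doses of 800 and 1200 mg/day; full absorption; linear kinetics.

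**Mean steady-state level** = (daily dose / 24) / CL.

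| Daily dose | Input rate | Mean at CL 0.4 | Mean at CL 5 | CL at which mean = 120 mg/L | CL at which mean = 12 mg/L |
|---|---|---|---|---|---|
| 400 mg | 16.67 mg/h | 41.7 mg/L | 3.3 mg/L | 0.14 L/h | 1.39 L/h |
| 800 mg | 33.33 mg/h | 83.3 mg/L | 6.7 mg/L | 0.28 L/h | 2.78 L/h |
| 1200 mg | 50 mg/h | 125 mg/L | 10 mg/L | 0.42 L/h | 4.17 L/h |

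The last two columns are the input rate divided by 120 or 12. For 120 mg/L the break-even clearance lies below the assumed range at 400 and 800 mg/day, and just inside its lower end at 1200 mg/day. For 12 mg/L it lies well inside the range at all three doses.

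**Daily dose giving a mean equal to the limit** = limit × CL × 24. For 120 mg/L: 120 × 0.4 × 24 = 1152 mg to 120 × 5 × 24 = 14,400 mg. For 12 mg/L: 115 mg to 1440 mg. Only the second range includes the protocol's 400 mg/day boundary.

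**Peaks.** A sample is not a mean, so I also took a one-compartment model with instantaneous absorption, which tends to overstate peaks: peak = (dose/V) / (1 − exp(−CL × tau/V)), with volume V assumed 20 to 50 L and tau 24 h for once-daily dosing. At CL 0.4 L/h:

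- 400 mg: 20/(1 − e^−0.48) = 52.5 mg/L at 20 L, down to 45.8 at 50 L.
- 800 mg: 40/(1 − e^−0.48) = 104.9 mg/L, down to 91.6.
- 1200 mg: 60/(1 − e^−0.48) = 157.4 mg/L, down to 137.4.

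At CL 0.5 L/h the 1200 mg peaks are 133.0 mg/L (20 L), 121.3 (30 L) and 112.5 (50 L). An 800 mg once-daily peak reaches 120 mg/L only with a still smaller volume: at 12 L (0.3 L/kg × 40 kg) and CL 0.4 L/h it is 66.67/(1 − e^−0.8) = 121.1 mg/L. Exceedance is thus confined to slow clearance combined with a high dose or a very small volume.

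**The case against.** Four points can fairly be made against this.

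1. **The pharmacokinetic inputs are assumed.** This stands. The lower clearance bound decides the 1200 mg/day result: at 0.5 L/h the mean is 100 mg/L, at 0.4 L/h it is 125 mg/L. A reader might infer that the printed limit can never discriminate at any maintenance dose; the table does not support that. The result for mean levels at 400 to 800 mg/day holds across the whole range.
2. **The calculation does not identify 12 mg/L.** This also stands. With CL from 0.4 to 5 L/h, any limit between 3.3 and 41.7 mg/L would correspond to a dose range containing 400 mg/day. The arithmetic shows that 120 mg/L is too high for its purpose. Preferring 12 mg/L rests on keeping the printed digits and changing only the unit.
3. **The number is not the only protection.** Correct. Criterion 11 requires 12 months of maintenance treatment and 3 months at a stable dose. The therapeutic-range recommendation carries no number and is unaffected, and investigator judgement applies. Section 6.5 adds: "It is recommended that additional increments in dose are evaluated with blood levels". Exclusion criteria 31 and 35 keep safety discretion.
4. **Exceeding the limit excludes nobody automatically.** Correct. It leads to local management and a discussion. A reader might infer that unsuitable subjects were randomized or that the trial's results are affected. The documents support neither: they do not report how many subjects take theophylline or at what levels, and the SAP does not use the figure.

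These points limit the size of the problem. They do not explain why a numeric trigger added on top of judgement should sit where it would almost never be met.

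**Conclusion.** The concern holds, as a probable unit error of small consequence. It is certain that the protocol prints 12 mg/dl three times, that this is 120 mg/L, and that nothing corrects it. It is very likely, but an inference, that 12 mg/L was meant. That the trigger would almost never operate rests on the assumed clearance of 0.4 to 5 L/h: mean levels peak at 41.7 mg/L for 400 mg/day and 83.3 mg/L for 800 mg/day, and reach 125 mg/L for 1200 mg/day only at the slowest clearance. The harm is limited to a study-physician discussion that may not take place and a level condition above 400 mg/day that has little effect. It is worth correcting because this is the only numeric theophylline level a site is given.

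**What to change.** The sponsor confirms the intended value and, if it is 12 mg/L, changes the unit to mg/L (µg/mL) in the section 6.5 text and in both places in the Xanthines row of Table 6. A clarification letter or the next amendment would do; no visit, procedure or analysis changes. Once the value is confirmed, the sponsor may review recorded levels of xanthine-treated subjects against the corrected limit, to see whether any discussion before randomization was missed. That review should wait for the confirmation, and its cost is limited to the subset on xanthines.
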